3.4.2 Inclusion Criteria

Subjects are required to meet the inclusion criteria presented in [Table 3.4.2-1](#).

Table 3.4.2-1 Inclusion Criteria	
1.	Informed consent prior to the initiation of any protocol-required procedures. In addition, the subject must provide informed consent at screening and must be able to understand that he or she can withdraw from the trial at any time. All informed consent procedures must be in accordance with the trial site's IRB/IEC and local regulatory requirements.
2.	Ability, in the opinion of the principal investigator, to understand the nature of the trial and follow protocol requirements, including the prescribed dosage regimens, tablet ingestion, and discontinuation of prohibited concomitant medications, to read and understand the written word in order to complete subject-reported outcomes measures, and to be reliably rated on assessment scales.
3.	Male and female outpatient subjects 18 to 65 years of age, inclusive, at the time of informed consent.
4.	Subjects with both a diagnosis of recurrent MDD, and in a current major depressive episode of ≥ 8 weeks in duration, as defined by DSM-5 criteria and confirmed by both the MINI and an adequate clinical psychiatric evaluation.
5.	Subjects must have reported a history for the current major depressive episode of an inadequate response to 1 or 2 adequate ADTs (as defined by the ATRQ). In addition, subjects must currently be taking a protocol-mandated antidepressant treatment at a dose defined in Section 3.2.1 and adequate duration (as defined by the ATRQ), and must not have reported $\geq 50\%$ improvement (as defined by the ATRQ). For subjects who are currently on an adequate dose of a protocol-mandated ADT but for an inadequate duration, the screening period may be used to achieve adequate duration. At Phase A baseline, all subjects must have either 2 or 3 documented inadequate responses to ADT in total for the current episode as defined by the ATRQ.
6.	Subjects with a HAM-D17 total score ≥ 18 at the screening and Phase A baseline visits.
7.	Subjects willing to discontinue all prohibited psychotropic medications to meet protocol-required washouts prior to and during the trial period.

ATRQ = Massachusetts General Hospital Antidepressant Treatment Response Questionnaire;

HAM-D17 = 17-item Hamilton Depression Rating Scale.

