Clinical laboratory tests (hematology, serum chemistry, urinalysis) ^c	X	X							X
Prolactin ^c		X							X
HbA1c ^c	X	X							

Protocol 331-201-00079

Assessment	Screening Day -42 to -3	Acute Treatment Phase								
		Phase A Base- line	Week 1 (± 2 days)	Week 2 (± 2 days)	Week 3 (± 2 days)	Week 4 (± 2 days)	Week 5 (± 2 days)	Week 6 (± 2 days)	Week 7 (± 2 days)	Week 8/ End-of Phase A or ET ^a (± 2 days)
TSH, with reflex to T ₄ if TSH is abnormal	X									
Coagulation parameters (PT, aPTT, INR)	X									
Blood alcohol ^g	X					X				X
Urine drug screen ^{g,h}	X					X				X
Urine pregnancy test (WOCBP only) ⁱ	X	X	X			X				X
SAS		X						X		
AIMS		X						X		
BARS		X						X		
C-SSRS ^j	X	X	X	X	X	X	X	X	X	X
Adverse events	X	X	X	X	X	X	X	X	X	X
Concomitant medications ^k	X	X	X	X	X	X	X	X	X	X
Other										
IMP dispensing			X	X	X	X	X	X	X	X
IMP accountability				X	X	X	X	X	X	X
		X								

anti-HCV = hepatitis C antibodies; aPTT = activated prothrombin time; AIMS = Abnormal Involuntary Movement Scale; BARS = Barnes Akathisia Rating Scale; HBsAg = Hepatitis B Surface Antigen; INR = International Normalized Ratio; PT = prothrombin time; SAS = Simpson Angus Scale.

^aThe End of Phase A visit will also be the ET visit for subjects who do not meet the response criteria. The investigator or site staff will provide relevant information for a blinded assessment of score-based response criteria for each subject. Whether or not a subject is an inadequate responder in Phase A will

Protocol 331-201-00079

be confirmed by eSource based on the score-based criteria defined in the blinded addendum to this protocol. The site will be notified of the subject's response status during the Weeks 6, 7, or 8 visits. Any subject who does not meet the criteria for adequate response will be discontinued from the trial. If a subject meets response criteria at Week 6 or 7 they will complete the Week 8 procedures and any remaining visits in Phase A will not be completed.

^bWashout of prohibited medications begins after signing the ICF and must comply with the required washout periods in [Table 4.1-1](#). Prohibited and restricted medications requiring a washout of at least 24 hours before the first dose of protocol-specified ADT in Phase A are listed in [Table 4.1-2](#) and [Table 4.1-4](#).

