3.7.1 Schedule of Assessments

3.7.1.1 Screening (Day -42 to Day -3)

The screening period begins after consent has been obtained. Although the screening period takes place between Day -42 and Day -3, subjects will participate in screening activities for 3 days. After the subject has provided consent, a subject number will be assigned. Screening evaluations will include the following:

- An assessment of all inclusion and exclusion criteria will be made to determine the subject's eligibility for the trial. Subjects cannot be enrolled until the CST review process has been completed and the site has received the final notification from the Medical Director or Clinical Scientist. Sites can expect that CST review and feedback to site on screening data will occur within 2 business days of receipt of full data set.
- Demographic data will be recorded.
- A general clinical evaluation will be performed, including concurrent medical conditions, medical history over the past 2 years, and medical history beyond 2 years which is considered to be clinically relevant per the investigator's judgment.
- Psychiatric history will be recorded, including the DSM-5 diagnosis of MDD that will be made by an adequately trained and experienced clinician and will be confirmed by the administration of the MINI ([Section 3.7.2.4.1](#)).
- Antidepressant history will be assessed by the Massachusetts General Hospital Antidepressant Treatment Response Questionnaire (ATRQ; [Section 3.7.2.4.3](#)). If the subject is on their current antidepressant for an inadequate duration at the time of the administration of the ATRQ, the subject may be contacted via telephone to collect their response to the current ADT once the subject is on this treatment for an adequate duration.
- Medications (including those that were taken within 30 days of screening) will be recorded. In addition, all prescription and non-prescription medications taken during the trial will be recorded as concomitant medications. Details of prohibited/restricted medications are provided in [Table 4.1-1](#), [Table 4.1-2](#), and [Table 4.1-4](#).
- Washout from prohibited concomitant medications, if applicable ([Table 4.1-1](#)).
- The investigator (or qualified designee) who is adequately trained will complete the 17-item Hamilton Depression Rating Scale (HAM-D17) ([Table 3.4.2-1](#); [Section 3.7.2.4.2](#)).

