4.1 Prohibited Medications

All subjects must agree to discontinue all prohibited medications during the screening period in order to meet the protocol-specified washout periods. [Table 4.1-1](#) provides the required duration of washout for selected prohibited medications. All other prohibited medications must be discontinued at least 24 hours before the first dose of IMP in Phase A.

Table 4.1-1 List of Medications Prohibited Before the Trial		
	Medication	Required Duration of Washout
1.	Antipsychotics (depot or long-acting injectable)	One full cycle plus 1/2 cycle
2.	Monoamine oxidase inhibitors	14 days
3.	Antipsychotics (oral)	7 days
4.	Benzodiazepines	7 days
5..	Hypnotics, including non-benzodiazepine sleep aids	7 days

Protocol 331-201-00079

Table 4.1-2 lists all medications prohibited during the trial, including exceptions, where appropriate.

Table 4.1-2 List of Medications Prohibited During the Trial	
1.	All psychotropic agents including, but not limited to, the following: a) Antipsychotics, including depot or long-acting injectable formulations b) Anticonvulsants c) Antidepressants other than those prescribed as IMP d) Mood stabilizers (ie, lithium) e) Benzodiazepines, except when used to manage treatment-emergent AEs such as agitation and anxiety (See Table 4.1-3) f) Hypnotics, including ramelteon and other non-benzodiazepine sleep aids, except for specific medications when used to manage treatment-emergent AEs related to insomnia ^a g) Stimulants h) Opioid analgesics, unless permission is obtained from the medical monitor. Permission for opioid use may be considered for a documented and clinically appropriate indication (eg, episodic pain condition, tooth extraction) if prescribed at a medically appropriate dose and frequency. i) Nutritional supplements and non-prescription herbal preparations with central nervous system effects (eg, St. John's Wort, omega-3 fatty acids, kava extracts, gamma-aminobutyric acid supplements, etc)
2.	Investigational agents

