3.	CYP2D6 inhibitors or CYP3A4 inhibitors and inducers. The medical monitor should be consulted for any questions regarding the potential for pharmacokinetic interactions with concomitant medications used by subjects during the trial. See Table 4.1-4 below provides a select list of CYP2D6 inhibitors and CYP3A4 inhibitors and inducers which are prohibited within 14 days prior to the first dose of brexpiprazole in Phase A or Phase B (as appropriate to the subject's point of entry into the trial) and for the duration of the trial.
4.	Barbiturates, except for the treatment of migraine headaches, provided that in the opinion of the investigator the dosing is medically appropriate.
5.	Varenicline

^aNon-benzodiazepine sleep aids (ie, zolpidem, zaleplon, zopiclone, and eszopiclone only) are permitted for the treatment of insomnia for up to 7 days total in Phase A, up to 7 days total in Phase B, and up to 7 days total in Phase C, but not on the same day as administration of a benzodiazepine, regardless of indication. For the non-benzodiazepine sleep aids, sites should only utilize 1 of the listed medications that are approved for this indication in their respective countries and the country-specific prescribing information is to be used to determine the maximum allowable daily dose for the treatment of insomnia. Non-benzodiazepine sleep aids must not be administered within 12 hours prior to scheduled efficacy and safety assessments, including EPS scales. Investigators are encouraged to delay scale administration until 12 hours have elapsed, if at all possible. However, if delaying administration of efficacy and safety scales is not feasible, the scales should still be administered and the use of the sleep aid documented, including a notation of the drug name, dose, and time of administration on the eSource.

Table 4.1-3 presents the protocol-specified oral benzodiazepines that can be used as rescue medication in this trial. Oral lorazepam and oral oxazepam are to be used, if available. In countries or at investigative sites where lorazepam and oxazepam are not

Protocol 331-201-00079

available, use of oral diazepam or oral clonazepam may be acceptable if prior authorization is obtained from the medical monitor.

Table 4.1-3 Oral Benzodiazepine Rescue Therapy During the Trial

Oral Benzodiazepine ^a	Maximum Allowable Weekly Dose (mg/week)		
	Phase A	Phase B	Phase C
Lorazepam ^b	12	10	6
Oxazepam ^b	180	150	90
Diazepam ^{b,c}	60	50	30
Clonazepam ^{b,c}	6	5	3

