^aBenzodiazepines must not be administered within 12 hours prior to scheduled efficacy and safety assessments, including EPS scales. Investigators are encouraged to delay scale administration until 12 hours have elapsed, if at all possible. However, if delaying administration of efficacy and safety scales is not feasible, the scales should still be administered and the use of benzodiazepine documented, including a notation of the drug name, dose, and time of administration on the eSource.

^bThe following guide should be used to determine approximate lorazepam equivalents:

1 mg lorazepam = 15 mg oxazepam = 0.5 mg alprazolam = 5 mg diazepam = 0.5 mg clonazepam.
Short-acting benzodiazepines are to be used whenever possible. The prescribed benzodiazepine should be discontinued as soon as the AE for which it was initiated subsides, as per the investigator's discretion to avoid any withdrawal effects.

^cIn countries or institutions where no short-acting benzodiazepines are commercially available, use of oral diazepam or oral clonazepam may be acceptable if prior authorization is obtained from the medical monitor.

Table 4.1-4 below provides a select list of CYP2D6 inhibitors and CYP3A4 inhibitors and inducers which are prohibited within 14 days prior to the first dose of brexpiprazole in Phase A or Phase B and for the duration of the trial.

Protocol 331-201-00079

Table 4.1-4 List of Medications Prohibited During the Trial: CYP2D6 Inhibitors and CYP3A4 Inhibitors and Inducers		
Selected CYP2D6 inhibitors^a	Selected CYP3A4 inhibitors	Selected CYP3A4 inducers
celecoxib hydroxyzine chloroquine methadone chlorpheniramine moclobemide clemastine clomipramine pyrilamine diphenhydramine quinidine terbinafine halofantrine tripelennamine	amiodarone fluvoxamine amprenavir indinavir aprepitant itraconazole chloramphenicol ketoconazole cimetidine nefazodone clarithromycin nelfinavir clotrimazole (if used orally) quinupristin/dalfopristin delavirdine ritonavir diltiazem saquinavir erythromycin troleandomycin fluconazole verapamil	carbamazepine oxcarbazepine phenytoin dexamethasone primidone efavirenz rifampin nevirapine St. John's Wort phenobarbital troglitazone

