anti-HCV = hepatitis C antibodies; aPTT = activated prothrombin time; ATRQ = Massachusetts General Hospital Antidepressant Treatment Response Questionnaire; AIMS = Abnormal Involuntary Movement Scale; BARS = Barnes Akathisia Rating Scale; CGI-S = Clinical Global Impression - Severity of Illness; C-SSRS = Columbia-Suicide Severity Rating Scale; ECG = Electrocardiogram; ET = End of trial; HBsAg = Hepatitis B Surface Antigen; IMP = Investigational medicinal product; INR = International Normalized Ratio; MADRS = Montgomery Asberg Depression Rating Scale; MDD = Major depressive disorder; MINI = Mini International Neuropsychiatric Interview; PT = prothrombin time; SAS = Simpson Angus Scale; T₄ = Thyroxine; TSH = Thyroid-stimulating hormone; US = United States.

^aThe End of Phase A visit will also be the ET visit for subjects who do not meet the response criteria. The investigator or site staff will provide relevant information for a blinded assessment of score-based response criteria for each subject. Whether or not a subject is an inadequate responder in Phase A will be confirmed by eSource based on the score-based criteria defined in the blinded addendum to this protocol. The site will be notified of the subject's response status during the Weeks 6, 7, or 8 visits. Any subject who does not meet the criteria for adequate response will be discontinued from the trial. If a subject meets response criteria at Week 6 or 7 they will complete the Week 8 procedures and any remaining visits in Phase A will not be completed.

^bWashout of prohibited medications begins after signing the ICF and must comply with the required washout periods in Table 4.1-1 of protocol. Prohibited and restricted medications requiring a washout of at least 24 hours before the first dose of protocol-specified ADT in Phase A are listed in Table 4.1-2 and Table 4.1-4 of protocol.

^cBlood samples for clinical laboratory tests must be drawn after a minimum 8-hour fast at the baseline visit and should be drawn after a minimum 8-hour fast at all other visits. If fasting blood samples are not feasible at visits other than the baseline visit, nonfasting blood samples may be collected. Vital sign and ECG assessments should be completed before any blood samples are collected.

Protocol 331-201-00079

^dMADRS and CGI-S can be collected remotely by telephone or video.

^eTo include measurement of height and waist circumference at screening and waist circumference at all other time points.

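### Two washout periods, 24 hours and 14 days, are given for the same CYP2D6 and CYP3A4 drugs before brexpiprazole starts in Phase A

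*Protocol*

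**What the plan says.** **Places that give 24 hours**

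- Protocol Table 3.7-1, footnote b, first requires compliance with the periods in Table 4.1-1. It then names Tables 4.1-2 and 4.1-4 as listing the medications "requiring a washout of at least 24 hours before the first dose of protocol-specified ADT in Phase A".
- COVID-19 addendum, Table 1.2-1, footnote b, repeats this: "before the first dose of protocol-specified ADT in Phase A are listed in Table 4.1-2 and Table 4.1-4 of protocol".
- Protocol Section 4.1, after pointing to Table 4.1-1 for selected washouts, sets a default: "All other prohibited medications must be discontinued at least 24 hours before the first dose of IMP in Phase A".

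**Places that give 14 days**

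- Table 4.1-2, item 3, on CYP2D6 inhibitors and CYP3A4 inhibitors and inducers: "prohibited within 14 days prior to the first dose of brexpiprazole in Phase A or Phase B (as appropriate to the" subject's point of entry.
- The sentence introducing Table 4.1-4: "prohibited within 14 days prior to the first dose of brexpiprazole in Phase A or Phase B and for the duration of the trial".

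**Places that might have settled it**

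- The screening procedures (Section 3.7.1.1) include "Washout from prohibited concomitant medications, if applicable", and that item refers only to Table 4.1-1.
- Inclusion criterion 7 reads "Subjects willing to discontinue all prohibited psychotropic medications to meet protocol-required washouts prior to and during the trial period", so it reaches psychotropic drugs only.

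**The concern.** For a subject taking a Table 4.1-4 drug at consent, the protocol gives two answers to when brexpiprazole may start. The shorter one sits in the schedule of assessments, on the washout row, where site staff are likely to look first.

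The protocol itself treats this interaction as a matter of exposure. Section 1.2.1 reports that potent CYP3A4 or CYP2D6 inhibitors roughly double brexpiprazole exposure and lengthen its half-life about 1.5-fold. Section 2.2 caps the doses of three ADTs for that reason. A site working to the 24-hour rule could dose a subject whom Table 4.1-2 bars. Two sites could also classify the same case differently as a deviation, since Section 3.13 counts breaches of eligibility or concomitant-medication criteria as significant.

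**Working it through.** The point is a comparison of texts, with simple arithmetic on the gap. It has no sample-size, power or alpha component, so there is no planned statistical figure to reproduce.

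**1. The rules side by side**

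| Place in the Protocol | Applies to | Period | Counted back from |
|---|---|---|---|
| Table 3.7-1 footnote b, and addendum copy | Tables 4.1-2 and 4.1-4 | at least 24 hours | first ADT dose in Phase A |
| Section 4.1 default | prohibited drugs not in Table 4.1-1 | at least 24 hours | first IMP dose in Phase A |
| Table 4.1-2 item 3 | CYP2D6 and CYP3A4 drugs | 14 days | first brexpiprazole dose |
| Introduction to Table 4.1-4 | CYP2D6 and CYP3A4 drugs | 14 days | first brexpiprazole dose |

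**2. Does Table 4.1-1 take these drugs out of the default?** Its five rows are depot antipsychotics, MAOIs, oral antipsychotics, benzodiazepines and hypnotics. There is no row for CYP inhibitors or inducers as a class, so the default covers the class.

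**3. Do the eligibility criteria settle it?** Exclusions 22 to 25 set windows for MAOIs, benzodiazepines and hypnotics, varenicline, and neuroleptics. None covers the CYP drugs as a class. The note after the exclusion table refers to Section 4, which contains both rules. Nothing states which prevails.

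**4. Size of the gap**

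- Drug continued until 24 hours before dosing: 14 - 1 = 13 days short.
- Drug stopped at consent, with the minimum 3-day screening (Section 3.1): 14 - 3 = 11 days short.
- Room for 14 days within the 6-week maximum: 42 - 14 = 28 days to spare.

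**5. Reach of the list.** As read from the PDF, Table 4.1-4 names 14 CYP2D6 inhibitors, 22 CYP3A4 inhibitors and 11 CYP3A4 inducers: 14 + 22 + 11 = 47 drugs. Fluoxetine, paroxetine and duloxetine are permitted ADTs controlled by dose caps (Table 4.1-4, footnote a) and fall outside the conflict.

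**The case against.** The strongest reply is that the rules can be obeyed together. A period of at least 24 hours is a floor, the 14-day rule is specific to a named class, and a 14-day washout satisfies every sentence. Footnote b also sends the reader to Table 4.1-2, where item 3 gives the 14 days. That table lists antipsychotics, benzodiazepines and hypnotics too, for which Table 4.1-1 requires 7 days or more, so 24 hours cannot be the full washout for everything footnote b names.

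There are safeguards as well:

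- The medication-recording item in Section 3.7.1.1 cites Tables 4.1-1, 4.1-2 and 4.1-4.
- Medications taken in the 30 days before consent are recorded, so recent use is visible.
- Item 3 directs questions about pharmacokinetic interactions to the medical monitor.
- Enrolment waits for the clinical surveillance team's review.

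On consequences, the protocol already accepts up to a 2-fold rise in exposure with the three CYP2D6-inhibiting ADTs. Phase A begins with 2 to 4 weeks of titration and weekly visits.

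Much of this stands as a limit on the risk. A careful reader would probably arrive at 14 days, and both the 13-day gap and the 47-drug count describe the wording, not an observed population. It does not remove the conflict. Footnote b separates drugs with Table 4.1-1 periods from drugs with a 24-hour period and puts the CYP list in the second group. Someone who applies that sorting as written breaches Table 4.1-2. The argument from accepted exposure also does not cover inducers, or a second inhibitor added to an inhibiting ADT.

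**Conclusion.** The concern holds. The protocol gives 24 hours in three places and 14 days in two for the same drugs, with nothing to say which governs. The possible shortfall is 13 days if the drug is taken until 24 hours before dosing, and 11 days if it stops at consent with minimum screening. Both figures assume a subject who is on a listed drug at consent and a site that applies the shorter rule.

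The number of such subjects cannot be derived from the documents, nor can the inhibition or induction remaining after 24 hours. The problem is confined to entry into Phase A and does not affect the randomized comparison, the event count or alpha. It is an operative safety rule that should be corrected, but it does not threaten the trial's conclusions.

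**What to change.** **Core change**

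- Add a row to Table 4.1-1 for the Table 4.1-4 drugs: 14 days before the first brexpiprazole dose in Phase A, with fluoxetine, paroxetine and duloxetine exempt as permitted ADTs.
- In footnote b of Table 3.7-1 and of addendum Table 1.2-1, take Table 4.1-4 out of the 24-hour sentence. Limit that sentence to Table 4.1-2 drugs with no longer period in Table 4.1-1.

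**Tidying, if the text is being amended anyway**

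- Count the footnote's period back from the first brexpiprazole dose. Subjects continue their ADT from screening, so the first ADT dose in Phase A is a poor reference point.
- Add varenicline to Table 4.1-1 at 5 days, to match exclusion 24.
- Delete the reference to Phase B from the washout wording in Table 4.1-2 item 3 and the introduction to Table 4.1-4, since subjects reach Phase B only through Phase A.

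**Cost.** The core change is a wording amendment to one table and two footnotes; the tidying touches two further sentences. No procedure is added. Some subjects on these drugs will need a longer screening period, within the 6 weeks already allowed.
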